5 DEMOGRAPHIC AND OTHER BASELINE CHARACTERISTICS

5.1 Demographics and Baseline Characteristics

Demographic variables include age, sex, race, and ethnicity. Baseline characteristics include American Society of Anesthesiologists (ASA) physical status, height, weight (kg), and BMI (kg/m^2). Demographics and baseline characteristics will be presented in a by-subject listing and summarized overall and by treatment group.

5.2 Medical/Surgical History

Medical and Surgical history, as collected at screening, will be coded using the Medical Dictionary for Regulatory Activities (MedDRA) version 20.1 to determine system organ class (SOC) and preferred term (PT). Medical histories will be presented in a by-subject listing.

Any events that occur prior to the study procedure will be categorized as medical history.

5.3 Prior and Concomitant Medications

Prior medications/therapies are those that stop prior to the start of the study drug administration. Any medication/therapy that stops at or after this time or with missing stop dates is considered concomitant medication/therapy.

Prior and concomitant medications are collected at screening and updated throughout the study as needed. Prior and concomitant medications will be coded using WHO/ATC classification index version September 2017. The number and percentage of subjects who take concomitant medications will be summarized by drug class and preferred term, overall and by treatment group, for the safety population.

All medications and non-medical therapies captured in CRFs will appear in data listings.

6 MEASUREMENTS OF TREATMENT EXPOSURE and COMPLIANCE

Because study medication is administered as a single dose at the study center by trained study personnel, compliance with respect to study medication will not be calculated. A listing of study drug administration and exposure data will be provided.

After completing the assessments through 48 hours after study medication administration, the diary for at-home use will be distributed to the subject to collect pain intensity (twice daily on NPRS) and pain medication through Day 15. Compliance with home diary use will be evaluated based on post-discharge home diary records. Compliance for each subject will be based on the number of days the subject participated in the outpatient study period, defined as:

Compliance (%) =

$$\frac{(N \text{ of non-missing NPRS recorded on Diary})}{(N \text{ of Expected NPRS from Diary})} \times 100$$

Where the N of expected NPRS records in the diary for each subject is calculated as 2 times the number of days the subject participated in the outpatient portion of the study. The number of days of participation will be calculated as the date of the Day 15 visit or the date of the last study visit (whichever is earlier) minus the date of discharge. NPRS recorded prior to a rescue use will not be included in this calculation of compliance.

For example, Subject A was discharged on Day 2, if this subject discontinues the study on Day 18, then the expected N of NPRS records on diary will be 36 (2 * (15-2)). Assuming Subject A had

CONFIDENTIAL

Page 16 of 32

10 NPRS available from his/her diary, then compliance for this subject would be 27.8% ((10/36) *100). However, if subject A had discontinued the study on Day 10 (prior to Day 15), then the expected N of NPRS for this subject would be 16 (2 * (10-2)) and compliance would be 62.5 % ((10/16) *100). A summary of compliance will be provided overall and by treatment group.

Compliance with recording an NPRS prior to rescue in the diary will be calculated as the number of NPRS recorded prior to taking rescue medications divided by the number of rescue medication uses recorded.

7 EFFICACY EVALUATION

7.1 Handling of Dropouts or Missing Data

All efforts will be made to minimize missing data. These efforts will include the following:

- Subjects are required to consent to continuous data collection even after discontinuation of study medication;
- Data collection will continue after subjects take rescue medication.

With the procedures above, it is expected that missing data will be minimal. Missing at random is expected to be a reasonable assumption for this dose-escalation study.

For subjects who take protocol allowed rescue medication a windowed last pain score carried forward (LOCF) will be used. The pre-rescue pain score will be used to impute scheduled assessments for 4 hours following the rescue use. Intermittent missing pain scores (due to subject sleeping, etc.) will not be imputed, and AUC will be calculated based on non-missing values. For subjects who drop out of the study prior to Day 15, or who are discontinued from efficacy and given SOC analgesics for inadequate pain relief, scheduled assessments will first be imputed using the worst prior pain score carried forward (WOCF) using the worst scheduled non missing pain score prior to drop out within the AUC period being calculated (e.g., if the AUC being calculated includes hours 12-24, the worst observed pain score between hours 12 and 24 will be used). As a sensitivity, the AUC will also be calculated where assessments after drop out will be imputed using LOCF, using the last scheduled non missing pain score prior to drop out.

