13.4.5. Analysis of Efficacy Measures

Efficacy variables will be summarized and analyzed.

The primary efficacy parameter is the area-under-the-curve (AUC) for NPRS scores across various time points, with adjustment for use of analgesic therapy/medication. The primary efficacy variable will be analyzed using an ANCOVA model with treatment as the main effect and baseline PI as the covariate. The overall treatment effect will be presented along with specific treatment arm differences and the two-sided 95% confidence intervals of the differences.

In this study, subjects are permitted to take rescue medication for analgesia. It is expected subjects randomized to placebo arm will take rescue medication often. During both inpatient and outpatient portions of the studies, the subjects will be instructed to record NPRS immediately prior (within approximately 15 min) to taking rescue medication.

For subjects who take rescue, the pre-rescue pain score will be used to impute scheduled assessments for 4 hours. Intermittent missing pain scores (due to subject sleeping, etc.) will not be imputed, and AUC will be calculated based on non-missing values. For subjects who drop out of the study prior to Day 15 due to Lack of Efficacy or Adverse Events, scheduled assessments may be imputed using worst prior pain score carried forward. All other subjects who drop out will have their last pain score carried forward.

Sensitivity analysis of the primary efficacy variable using different methods of imputation for rescue medication may also be performed.

Additional sensitivity analysis with different missing value imputation methods for subjects who drop out of the study may also be performed.

All imputation methods for pain intensity will be documented in the SAP.

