7.4.1 AUC Outcomes

All AUC calculations will be done using the standard trapezoidal rule

$$AUC = \sum_{i=0}^x \left(\frac{NPRS_i + NPRS_{i+1}}{2} \right) * (T_{i+1} - T_i)$$

Where: $NPRS_i$ = NPRS at time i , and $(T_{i+1} - T_i)$ is the Time difference in hours between time i and time $i+1$.

Missing NPRS will be handled as discussed in Section 7.1.

AUC values will be analyzed using a 1-factor (treatment) analysis of variance (ANOVA) model with treatment as the main effect. In addition to the individual comparisons between each of the five CA-008 groups and the placebo group, the test for a linear trend across dose groups will be carried out using the scores 0, 0.5, 1.0, 2.0, 3.0 and 4.2 for the placebo group and the five active groups, respectively.

The AUC analyses will be presented in a summary table with standard summary statistics for each dose cohort and placebo as well as active vs. placebo mean differences, standard errors, confidence intervals and comparison p-values as appropriate. Comparisons of individual dose cohorts for dose response may be presented for certain secondary AUC endpoints.

Mean NPRS scores over time (in-clinic and diary) will be graphed over time by dose cohort. NPRS over time by each subject may also be displayed graphically as warranted. The individual NPRS and the computed AUC variables will be listed for all individual subjects.

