7.4.2 Average Daily NPRS score of 2 daily diary assessments

The Average Daily NPRS scores will be computed for each subject using the NPRS scores recorded in the take-home diary from study days 3 – 15.

The Average Daily NPRS will be the average of the AM and PM scores within each day. If individual AM or PM NPRS scores are missing, the score that is present will be used as the daily average. If both scores are missing for any day, then that day will not have a daily average. The mean across all subjects of the average daily scores on each day will be graphed by day and

dose cohort. If rescue medication was taken within 4 hours of the AM or PM PI assessment, it will be replaced with the pre-rescue NPRS (if available) in the daily average.

The average daily NPRS scores will be analyzed using the same type of ANOVA model as described in Section 7.4.1 at each time point. In addition, actual date/time NPRS assessed over the outpatient period from T48h onward will be used to calculate AUC between 24 hours and Week 1 and between 24 and Week 2 and compared versus placebo.

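### The rescue rule replaces scheduled NPRS scores for 4 hours with the pre-rescue score even when the observed score is higher, so recorded worse pain is lowered in the AUC

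*SAP*

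**What the plan says.** SAP 7.1 names the method: "For subjects who take protocol allowed rescue medication a windowed last pain score carried forward (LOCF) will be used". It then gives the rule: "The pre-rescue pain score will be used to impute scheduled assessments for 4 hours following the rescue use". Protocol 13.4.5 has the same rule: "For subjects who take rescue, the pre-rescue pain score will be used to impute scheduled assessments for 4 hours". Neither text adds a condition for an observed score that exceeds the pre-rescue score.

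The verb is impute, but three statements show that the rule acts on scores that exist:

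- SAP 7.1 on collection: "Data collection will continue after subjects take rescue medication".
- SAP 7.1 on ordinary gaps: "Intermittent missing pain scores (due to subject sleeping, etc.) will not be imputed, and AUC will be calculated based on non-missing values". The rescue rule is therefore not a gap filler.
- SAP 7.4.2, on an AM or PM diary score with rescue within 4 hours: "it will be replaced with the pre-rescue NPRS (if available) in the daily average".

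SAP 7.4.1 fixes the AUC formula: "All AUC calculations will be done using the standard trapezoidal rule".

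**The concern.** A rule of this kind is normally there to stop the effect of rescue from being credited to the study treatment. That purpose is my inference; neither document states it. Where the score falls after rescue, carrying the pre-rescue value forward does that job. Where the score rises despite rescue, the rule does the opposite and replaces the worse recorded pain with a milder earlier value.

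Apart from measurement noise, the lower value is wrong for either plausible target. If the target is pain as experienced, the observed score is the answer. If it is pain without rescue, and rescue does not itself increase pain, the answer is at least the observed score.

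Rising pain is realistic here. All subjects receive a bupivacaine block, and protocol 5.1.4 puts local-anaesthetic relief at 6 to 24 hours. Wear-off therefore falls inside AUC(0-12) and AUC(12-24), both listed in SAP 7.3. Rescue is encouraged from NPRS 4, which leaves up to 6 points of the scale above the carried value.

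**Working it through.** The plan gives no figure for this point, so there is none to reproduce.

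**Inputs**

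- NPRS times in hours: 0.25, 0.5, 0.75, 1, 2, 4, then every 4 to 48 (protocol 7.1.5).
- Trapezoidal rule (SAP 7.4.1); 4-hour window (SAP 7.1).
- Rescue allowed every 2 hours in clinic (protocol 9.1.3), with a new NPRS within 15 minutes before each use (protocol 7.1.5).
- All pain scores below are illustrative assumptions, because the documents contain no pain data.

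**Loss per overwritten score.** Let d be the observed minus the pre-rescue score, and let h1 and h2 be the gaps to the neighbouring scores. If only scheduled scores enter:

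- Interior time: loss = d × (h1 + h2)/2. From hour 8 both gaps are 4 h, so the loss is 4d. At hour 4 the gaps are 2 h and 4 h, so it is 3d.
- Boundary at hour 12 or 24: loss = d × 4/2 = 2d from each adjoining window.

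For d of 1 to 4 points, an interior score from hour 8 loses 4 to 16 NPRS-hours.

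**One interior substitution.** Scores 0, 0, 0, 0, 1, 3, 8, 6 at 0.25 to 12 h:

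- Observed: 0.5 + 4 + 22 + 28 = 54.5.
- Rescue before hour 8 at a score of 4, so 8 becomes 4: 0.5 + 4 + 14 + 20 = 38.5.
- Loss: 16, or 16/54.5 = 29%.

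**One boundary substitution.** Score 0 through hour 2, then 1, 3, 8, 7, 6, 5 at hours 4 to 24; rescue at hour 10 with pre-rescue score 4:

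- AUC(0-12): observed 1 + 8 + 22 = 31; under the rule 1 + 8 + 14 = 23.
- AUC(12-24): observed 30 + 26 + 22 = 78; under the rule 22 + 26 + 22 = 70.
- If the pre-rescue score also enters the trapezoid, AUC(0-12) goes from 28 to 24. The loss in AUC(12-24) stays at 8, because no pre-rescue score lies in that window.

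**Repeated rescue.** Scores 4, 6, 8, 9, 9 at hours 8 to 24, with rescue just after each scheduled score from hour 8 to 20:

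- AUC(12-24) observed: 28 + 34 + 36 = 98.
- Under the rule the scores become 4, 6, 8, 9: 20 + 28 + 34 = 82, a loss of 16 (16%).
- With pre-rescue scores in the trapezoid: 97.85 to 91.75, a loss of 6.1.

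**Overlapping windows.** In the first example, suppose the subject takes rescue again just after scoring 8 at hour 8. The 8 is carried to hour 12, but hour 8 still lies in the earlier window:

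- Hour 8 overwritten: 0.5 + 4 + 14 + 24 = 42.5.
- Hour 8 left standing: 0.5 + 4 + 22 + 32 = 58.5.

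The SAP does not say which applies.

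**Falling pain.** Observed 3, 3, 3, 3 at hours 12 to 24, with pre-rescue scores 6, 5 and 5 carried to hours 12, 16 and 24:

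- Observed AUC(12-24) = 36.
- Under the rule: 22 + 16 + 16 = 54. Taking the higher score also gives 54.

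**Diary average (SAP 7.4.2).** With both daily scores present, lowering one by d lowers that day's mean by d/2.

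**The case against.** The strongest objection is to any claim about direction. A reader might infer that the rule shrinks the estimated drug effect, because protocol 13.4.5 expects frequent rescue on placebo. The documents do not support that step. They say nothing about a steeper rise on placebo, and protocol 5.1.2 describes immediate hyperalgesia and limited early benefit with capsaicin, with a similar profile expected for CA-008. Post-rescue rises could be as common on active drug in the early windows. This objection stands in full.

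A reader might also take 29% as typical, or conclude that the rule lowers AUC overall. Neither follows. The 29% comes from a favourable single case, and rescue every 2 hours with a fresh score can shorten the time for which an old low score is carried. The falling-pain example moves the other way.

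Other objections stand in part:

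- Subjects without adequate relief leave the efficacy portion, and later scores are then imputed from the worst prior score. That does not restore scores overwritten before they left.
- Protocol 13.4.5 allows a rescue-imputation sensitivity analysis, but as an option. The SAP's only AUC sensitivity analysis, reflected in Tables 14.2.1.1 and 14.2.1.2, varies dropout imputation. Individual scores are listed, but no AUC from observed scores is planned.
- Taking the higher of two scores has its own bias. With equal true pain and independent normal errors of SD 1 to 2 points (an assumption), the expected excess is SD/√π, or 0.56 to 1.13 points per affected score. It accrues most where rescue is most frequent.
- Windowed LOCF is prespecified consistently in both documents, so replacing it is partly a matter of judgement.

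**Conclusion.** The point holds in limited form. As written, the rule lowers recorded pain whenever a scheduled score within 4 hours after rescue exceeds the pre-rescue score. From hour 8 of the inpatient schedule the cost is 4 NPRS-hours per point at an interior time, or 2 per point in each adjoining window at hours 12 and 24. This assumes that only scheduled scores enter the trapezoid. The SAP does not say whether pre-rescue scores enter too; if they do, the loss is generally smaller but does not vanish.

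The conclusion rests on reading impute as overwrite, which the continued collection, the no-imputation rule for gaps and the wording of SAP 7.4.2 support. How often scores exceed the pre-rescue value, the net effect on AUC and the direction of any bias in the treatment contrast cannot be determined from the documents.

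The consequence is modest. Efficacy is exploratory, p-values are nominal and the primary objectives are safety and pharmacokinetics. With 6 active subjects per cohort, however, one subject's 16-unit loss moves a cohort mean by 16/6 = 2.7 NPRS-hours.

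**What to change.** Before database lock:

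1. State in SAP 7.1 and 7.4.2 that, within the 4-hour window, the pre-rescue score replaces a scheduled score only when the observed score is not higher; that is, use the higher of the two.
2. State which pre-rescue score applies when rescue windows overlap, and whether pre-rescue scores enter the trapezoid.
3. Report AUC under the current windowed LOCF rule and AUC from observed scores as sensitivity analyses.
4. Record the change from protocol 13.4.5 in SAP section 12.

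The cost is a few SAP sentences, a maximum in the derivation code and additional AUC tables. Data collection and patient management are unaffected. The price is the upward bias described above, which the two sensitivity analyses would make visible.

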8. Neurosensory Exam of the Foot / Great toe (bilateral): 24 hours (±2 hours) and 48 hours (±4 hours) after study drug administration.
9. Clinical Laboratory tests (chemistry/coagulation, hematology and urinalysis) should be performed at 1.5 hours (±0.5 hour) after administration of study medication
10. NPRS pain assessments at: 0.25, 0.5, 0.75, 1, 2, 4, 8, 12 hours, then every 4 hours (if awake at time of assessment) until discharge or ET, and prior to supplemental pain therapy or medication. NPRS assessments between 00:00 and 06:00 may be skipped if the subject is sleeping; however, consecutive assessments may not be skipped, and the Hour 12, Hour 24, and Hour 48 assessments must be completed even if the subject is asleep. There will be a ±5 minute window allowed for the collection of each pain intensity assessment in the first 4 hours after the end of surgery, after which will be a ±15 minute window allowed.
11. 2x/day through Day 15
12. Review Subject Diary instructions with subject
13. Dispense Subject Diary
14. Collect Subject Diary

Clinical Trial Protocol
CA-PS-2017-101

Concentric Analgesics, Inc.
CONFIDENTIAL

- ¹⁵. Collect blood samples. The time points for collection are at baseline (before dosing), and at 5 minutes, 15 minutes, 30 minutes, 45 minutes, and 1, 1.5, 2, 2.5, 3, 3.5, 4, 6, 8, 12, 16, 24, 36, and 48 hours after dosing. There will be a ± 2 minute window allowed for the 5 and 15 minute collections, a ± 5 minute window allowed for collections through 4 hours, and a ± 15 minute window for collections through 48 hours.

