- Change from baseline is defined as post-baseline value minus baseline value.
- Duration of an AE will be computed in days for AEs lasting longer than 24 hours, and as hours for AEs lasting less than 24 hours. Duration in hours will be calculated as the stop date/time of the event minus the start date/time. Duration in days will be calculated by using stop date minus the start date +1 if AE occur on or after taking study medication. If AE occur prior to the study medication, then the duration will be calculated by using stop date minus the start date; If reported as ongoing at the time of database lock, the duration will be calculated using the date of the last visit or the last date of any AE for the subject in the database, whichever is later. Missing dates will be imputed as described in Table 8-1.
- The number of days in the study is computed as: [Date of study completion or withdrawal minus the date of study drug administration (Day 1)] + 1.
- If duplicate values are obtained at a given visit (e.g., repeated vital sign measurements), the last value will be used unless it is noted that the measurement was in error for that value. Values that compromise interpretation will not be used in summaries (e.g., values that were obtained post-dose will not be summarized as pre-dose values).
- If a pre-rescue NPRS is recorded in the same minute as a rescue medication is recorded, the NPRS will be assumed to have occurred PRIOR to the administration of rescue.
- If a subject experiences inadequate analgesic relief and are discontinued from the efficacy portion of the study the date/time of the discontinuation will be assumed to be the date/time of the start of standard of care analgesic rescue.

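### SAP 7.1 limits the drop-out carry-forward to scheduled pain scores, so the score taken before standard-of-care analgesia may be lost and some treatment failures' AUC understated

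*SAP*

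**What the plan says.** SAP 7.1 applies its drop-out rule to subjects who leave the study before Day 15 "or who are discontinued from efficacy and given SOC analgesics for inadequate pain relief". The main analysis (WOCF) imputes their later scheduled assessments "using the worst scheduled non missing pain score prior to drop out within the AUC period being calculated". The sensitivity analysis (LOCF) does so "using the last scheduled non missing pain score prior to drop out". The WOCF sentence then gives an example for hours 12 to 24, in which "the worst observed pain score between hours 12 and 24 will be used".

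SAP 3 fixes the moment of failure: "the date/time of the discontinuation will be assumed to be the date/time of the start of standard of care analgesic rescue". Protocol Table 1, footnote 10, lists NPRS at fixed times "until discharge or ET, and prior to supplemental pain therapy or medication". Protocol 10.4.1 likewise treats the score within 15 minutes before pain medication as additional to the timed list, and SAP 6 leaves pre-rescue scores out of the count of expected diary records.

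A separate rule in SAP 7.1 uses the pre-rescue score for scheduled times in the 4 hours after rescue, but only for rescue that the protocol allows. Protocol 9.1.3 and SAP 2.2 place standard-of-care analgesia outside that regimen.

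Protocol 13.4.5 says that for drop-outs due to lack of efficacy or adverse events, "scheduled assessments may be imputed using worst prior pain score carried forward". It sets no limit to scheduled scores. SAP 12 lists no change on this point.

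**The concern.** The NPRS that documents a treatment failure is normally the unscheduled one taken before standard-of-care analgesia. Under the operative wording it cannot be a donor for WOCF or LOCF. Because both analyses share the restriction, the sensitivity analysis would not expose its effect.

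The pattern that matters is plausible here. Every subject has a bupivacaine block (protocol 7.1.2.2), and protocol 5.1.4 puts relief from local anesthetics at 6 to 24 hours. Scheduled scores are 4 hours apart from hour 4, and one may be skipped in sleep. A subject can therefore have only low scheduled scores in the AUC period and then fail between two assessments. With 6 subjects per dose, one such subject can move a group mean visibly. Protocol 13.4.5 names the AUC as the main efficacy parameter.

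**Working it through.** The plan gives no figure for this rule, so there is nothing to reproduce. The check applies the trapezoidal formula of SAP 7.4.1, the sum of (NPRS_i + NPRS_i+1)/2 × (T_i+1 − T_i), to illustrative subjects.

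**Inputs.** From the documents: scheduled times 0.25, 0.5, 0.75, 1, 2, 4, 8 and 12 h (protocol 10.4.1), 6 active subjects per cohort, and placebo pooled over five cohorts (SAP 3), 5 × 2 = 10. Assumed: scores 0, 0, 0, 0, 1, 2 through hour 4; an allowed oxycodone dose at 5 h with pre-rescue score 8; standard-of-care analgesia at 7.5 h with pre-rescue score 9.

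**Two open points.** (a) Hour 8 falls after discontinuation and also within 4 hours of the 5 h dose. The SAP does not say which rule fills it. It describes WOCF as done first, but this reads as a contrast with the LOCF sensitivity analysis, not as a ranking over the rescue rule. (b) SAP 7.2 uses actual collection times and the 7.4.1 formula is not confined to scheduled scores, so pre-rescue scores may or may not enter as points of their own.

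**Scheduled points only.** Hours 0.25 to 4 contribute 0 + 0.5 + 3 = 3.5. The rest is 2(2 + x8) + 2(x8 + x12).
- Drop-out rule overrides (x8 = x12 = 2): 3.5 + 8 + 8 = 19.5
- 4-hour rule fills hour 8 (x8 = 8, x12 = 2): 3.5 + 20 + 20 = 43.5
- Failure score carried (x8 = x12 = 9): 3.5 + 22 + 36 = 61.5

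**Pre-rescue scores also entered at 5 and 7.5 h.** Hours 4 to 7.5 contribute 5 + 21.25 = 26.25. The rest is 0.25(9 + x8) + 2(x8 + x12).
- (2, 2): 3.5 + 26.25 + 2.75 + 8 = 40.5
- (8, 2): 3.5 + 26.25 + 4.25 + 20 = 54.0
- (9, 9): 3.5 + 26.25 + 4.5 + 36 = 70.25

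| Reading | AUC under SAP 7.1 | Failure score carried | Shortfall | ÷ 6 | ÷ 10 |
|---|---|---|---|---|---|
| Scheduled points, drop-out rule overrides | 19.5 | 61.5 | 42 | 7.0 | 4.2 |
| Scheduled points, 4-hour rule first | 43.5 | 61.5 | 18 | 3.0 | 1.8 |
| Pre-rescue points in, drop-out rule overrides | 40.5 | 70.25 | 29.75 | 5.0 | 3.0 |
| Pre-rescue points in, 4-hour rule first | 54.0 | 70.25 | 16.25 | 2.7 | 1.6 |

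**Longer periods.** Assume hour-24 score 1, oxycodone at 25 h and standard of care at 27 h, both with pre-rescue score 8. Even with the 4-hour rule first, AUC(24-96) = 18 + 18 + 64 = 100 (mean 100/72 = 1.4), against 18 + 68 × 8 = 562 (mean 7.8) with the 8 carried. Entering the pre-rescue points adds 10.5 to both, so the gap of 462 stays.

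**When it bites.** No high scheduled score may fall between pain onset and standard-of-care start. If onset is uniform within a 4 h gap (assumed), the share with no scheduled score in between is 1 − delay/4: 75%, 50%, 25% and 0% for delays of 1, 2, 3 and 4 h. In an 8 h gap it is 75% at 2 h and 50% at 4 h.

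**The case against.** The strongest reply is that the SAP's own WOCF example refers to observed scores, and a pre-rescue NPRS is observed. So it cannot be said that the score is excluded on every reading of the main analysis. That stands, but it makes the SAP inconsistent rather than clear: two programmers could derive different AUCs for one subject. The LOCF sentence has no such example.

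A reader might infer that failures are generally scored as nearly pain-free. The documents do not support this. In the AUC(0-12) illustration the lowest value, 19.5 (mean 19.5/11.75 = 1.7), needs the drop-out rule to override the 4-hour rule and only scheduled points to enter the trapezoid; the other readings give means of 3.4 to 4.6. A mean near 1 in a long period needs the particular pattern assumed above. One high scheduled score in the period before discontinuation removes the problem from WOCF.

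A reader might also infer that the error hides a drug effect because placebo subjects are expected to take rescue often. Taking rescue is not failing on it. Protocol 9.1.3 says the oxycodone regimen was adequate for more than 90% of placebo subjects in earlier bunionectomy studies, which implies fewer than 0.10 × 10 = 1 expected failure among the pooled placebo subjects. The direction is open.

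Nor are failures concealed. They appear in disposition (SAP 4.2), opioid use counted two ways (7.4.3), Fisher's tests on drop-out for inadequate analgesia (7.4.4), time to rescue (7.4.7), subject listings and a figure without drop-out imputation.

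Finally, protocol 13.4.5 is permissive and leaves imputation detail to the SAP. The SAP is therefore narrower than the protocol wording rather than in breach of it.

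**Conclusion.** The point holds as a moderate issue. As written, SAP 7.1 keeps the score that shows the failure out of both carry-forward analyses, while its own example and protocol 13.4.5 point the other way. Where scheduled scores in the period are low and failure comes between assessments, the AUC is understated. In the illustration this is about 16 to 42 NPRS-hours of AUC(0-12) for one subject: about 3 to 7 on a 6-subject dose mean, or 1.6 to 4.2 on the pooled placebo mean. The gap can be larger over longer periods.

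These sizes rest on assumed scores and times; the documents give no score distribution or failure rate for this study. They do not support a claim of bias in a known direction, or a claim that the trial's conclusions are at risk. Efficacy is secondary, p-values are nominal without formal testing (SAP 7.4), and escalation follows safety review by the DMC (SAP 11).

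**What to change.** In SAP 7.1, replace *scheduled* in both donor definitions so that every observed NPRS before drop-out is eligible, including pre-rescue scores and the score before the first standard-of-care analgesic. WOCF would take the worst of these within the AUC period and LOCF the last. This agrees with the SAP's own example and with protocol 13.4.5.

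Also state which rule governs a scheduled time that falls both after efficacy discontinuation and within 4 hours of an allowed rescue dose. Removing one word would leave that gap open. It would help to say in SAP 7.4.1 whether pre-rescue scores enter the trapezoid as points. If the restriction to scheduled scores is intended, list it in SAP 12 with a reason.

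The cost is a short wording change before database lock and one more derivation rule. The scores are already collected and nothing changes for patients. The small downside is slightly higher imputed AUCs for failures.
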